6.2.2 PK/PD relationships

The exploratory analysis of the relationship between pharmacokinetic and pharmacodynamic measures will not be performed because of low sample size resulting from study termination.

6.3 Exploratory objectives

The planned analyses for bronchiectasis exacerbation will not be performed due to study termination.

6.3.1 Variables

The exploratory endpoints are:

- Change from baseline in sputum bacterial colonization measured by 16S rRNA PCR.
- Changes from baseline in SGRQ, and EQ-5D-3L
- Change from baseline in HRCT endpoints for distribution of mucus (whole lung and regional)
- Change from baseline of markers in blood and sputum including:
 - serum hsCRP
 - blood inflammatory cells (e.g. neutrophils, eosinophils)
 - sputum inflammatory proteins (e.g. IL-6, IL-8)

6.3.2 Descriptive analyses

Summary statistics will be provided by treatment group and visit for all exploratory endpoints, if data allows.

7 Statistical methods for safety and tolerability data

For all safety analyses, the safety set will be used. All listings and tables will be presented by treatment group.

Safety summaries include only data from the on-treatment period with the exception of baseline data which will also be summarized where appropriate (e.g. change from baseline summaries). In addition, a separate summary for death including on treatment and post treatment deaths will be provided. In particular, summary tables for adverse events (AEs) will summarize only ontreatment events, with a start date during the on-treatment period (treatment-emergent AEs).

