As the completed thorough QT study (CQBW251A2105) indicated that QBW251 at 300 mg b.i.d. did not have clinically relevant effects on studied ECG parameters, single ECGs pre- and post-dose at Tmax will be performed at visits on Day 1, Day 28, Day 56 and Day 84 (end of treatment). These assessments will be complemented by PK sampling (trough and Cmax) on the matching timepoints, at visits on Day 1, Day 28, Day 56 and Day 84.

The morning dose on Day 84 will be the final dose administration for this treatment period. End of treatment assessment, e.g. safety assessment, lung function assessments and PROs will be performed on Day 84.

If spontaneous sputum collection is not possible at Day 84, site needs to reschedule the visit within 3 days after Day 84 and subject must continue to take study medication. If spontaneous sputum collection attempts are still not satisfactory, investigator may take decision to collect sputum sample after induction by the inhalation of saline. Other assessments that have been completed on Day 84 do not need to be repeated.

A second HRCT will be performed at Day 84 after the morning dose of study medication at site. If the HRCT can't be performed at Day 84 for any reason, the assessment needs to be planned within approximately the 3 coming days and patient must continue to take study medication.

In case of symptom deterioration (via e-diary alert), subjects must visit their study center to determine whether exacerbation criteria have been met and an immediate antibiotic treatment may be necessary. In addition, other markers of inflammation such as fibrinogen in blood will be taken to gain more information on systemic inflammation and sputum sample collection to determine if there are changes in pathogen or bacterial load that may have resulted in the exacerbation. Subjects experiencing an exacerbation during the treatment period will continue with the study treatment along with the standard of care (SOC) therapy for an exacerbation (i.e. antibiotics).

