### End of Study (EoS) visit (Day 91):

Approximately one week upon completion of the treatment period, subjects will be invited to the center for study visit completion (EOS) assessments.

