Physical Examination 	S	S									S							S		S		S		S
Body Height	Χ																							
Body Weight	Χ																					Χ		
Body Temperature	Χ	Х	Χ								Х							Χ		Χ		Х		X
Blood Pressure	Х	Х	Χ								Х							Χ		Χ		Х		Χ
Pulse rate	Χ	Х	Χ								Х							Χ		Χ		Χ		Χ
Clinical Chemistry 	Х		Χ								Х							Χ		Χ				Χ
Coagulation 	Χ		Χ								Х							Χ		Χ				X
Hematology	Х		Χ								Х							Χ		Χ				Χ
Urinalysis	Х		Χ								Х							Χ		Χ				Χ
Pregnancy and assessments of fertility 	Х		Х								Х							Х		Х		Х		Х

EPOCH	Scree	ning	Treatment														End o	f Study	Unscheduled					
Visit Name	Screening	Baseline 													End of Study	Safety Follow Up	Unscheduled							
Visit Numbers 	1	20	100							110 	120							130 140			40	1999		150
Days	-42 to -1	1 -3 +1		1						14	28 ±3								6 3	84 ±3		91 ±3	114 ±3	•
Weeks			1				2	4						8			12 1		17	-				
Time (post-dose)	-	-	0h4	1h	2h	3h	4h	6h	8h	-	0h 	1h	2h	3h	4h	6h	8h	0h4	3h	0h 	3h	-	-	-
Electrocardiogram (ECG) 	Х		Х			X					Х			Х				X	Х	Х	Х	Х		Х
St. George's Respiratory Questionnaire (SGRQ)		Х																		х				
EQ-5D-3L		Х																		Х				
Quality of Life Questionnaire for Bronchiectasis (QOL-B)		х									х							X		x				
eDiary										Х														X
EXACT-PRO 	X 											Χ												X
HRCT 	X 																			X 				
Spirometry	Х		Χ								Х							Χ		Х				X
Spirometry reversibility test	Х																							
Oxygen Saturation	Χ																							
Sputum bacterial load 	Χ	Х									Х							Χ		Х				X
Sputum 16S rRNA PCR		Х									Х							Χ		Х				
Exploratory Biomarkers in Sputum		Х									х							Х		Х				
Exploratory sputum bacterial profile		Х																		х				

EPOCH	Scree	ening									Tre	atm	ent									End of Study		Unscheduled
Visit Name				Treatment													End of Study	Safety						
Visit Numbers 	1	20		100						110 	120							1:	30	140		1999		150
Days	-42 to -1	1 -3 +1		1					14	28 ±3							56 ±3		84 ±3		91 ±3	114 ±3	-	
Weeks						1				2	4			8		12		13	17	-				
Time (post-dose)	-	-	0h 	1h	2h	3h	4h	6h	8h	-	0h4	1h	2h	3h	4h	6h	8h	0h4	3h	0h 	3h	-	-	-
Exploratory Biomarkers in Blood		Х									Х									Х				

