# 10.1.3 SAE reporting

To ensure subject safety, every SAE, regardless of causality, occurring after the subject has provided informed consent and until 30 days following the last administration of study treatment must be reported to Novartis safety immediately, without undue delay, but under no circumstances later than within 24 hours of obtaining knowledge of the events (Note: If more stringent, local regulations regarding reporting timelines prevail). Detailed instructions regarding the submission process and requirements are to be found in the investigator folder provided to each site.

- Screen Failures (e.g. a subject who is screened but is not treated or randomized): SAEs occurring after the subject has provided informed consent until the time the subject is deemed a Screen Failure must be reported to Novartis
- Baseline Failures (e.g. A subject who is screened but not randomized/treated after the baseline visit): SAEs collected between time subject signs ICF until time that subject is determined to be a baseline failure.
- Randomized OR Treated Subjects: SAEs collected between time subject signs ICF until 30 days after the subject has discontinued or stopped study treatment.

All follow-up information for the SAE including information on complications, progression of the initial SAE and recurrent episodes must be reported as follow-up to the original episode immediately, without undue delay, and under no circumstances later than 24 hours of the investigator receiving the follow-up information (Note: If more stringent, local regulations regarding reporting timelines prevail). An SAE occurring at a different time interval or otherwise considered completely unrelated to a previously reported one must be reported separately as a new event.

If the SAE is not previously documented in the Investigator's Brochure or Package Insert (new occurrence) and is thought to be related to the study treatment, a CMO & PS Department associate may urgently require further information from the investigator for health authority reporting. Novartis may need to issue an Investigator Notification (IN) to inform all investigators involved in any study with the same study treatment that this SAE has been reported.

Suspected Unexpected Serious Adverse Reactions (SUSARs) will be collected and reported to the competent authorities and relevant ethics committees in accordance with EU Guidance 2011/C 172/01 or as per national regulatory requirements in participating countries.

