#### 12.5.2 Safety endpoints

All safety endpoints will be analyzed based on safety set and will be summarized by actually received treatment group.

Safety summaries (tables, figures) include only data from the on-treatment period with the exception of baseline data which will also be summarized where appropriate (e.g. change from baseline summaries). In addition, a separate summary for death including on treatment and post treatment (30 days after the last actual administration of study treatment) deaths will be provided. In particular, summary tables for adverse events (AEs) will summarize only ontreatment events, with a start date during the on-treatment period (treatment-emergent AEs).

The on-treatment period lasts from the date of first administration of study treatment to one week after the date of the last actual administration of any study treatment.

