Concomitant medications and significant non-drug therapies prior to and after the start of the study treatment will be listed and summarized according to the Anatomical Therapeutic Chemical (ATC) classification system, by treatment group.

Vital signs

Records taken at baseline visit will be considered as baseline value. Otherwise, records take at Day 1 will be considered as baseline value. Vital sign data for all subjects will be listed by treatment group, subject and visit/time, and abnormalities will be flagged. The normal range of vital signs are:

Oral body temperature: 36.5-37.5 °C
Systolic blood pressure: 90-140 mm Hg
Diastolic blood pressure: 50-90 mm Hg

• Pulse rate: 50 - 100 bpmD

ECG evaluations

ECG data will be collected at scheduled visits in single ECG or triplicate ECGs. If triplicate ECGs are performed, then average of the non-missing values of the 3 measurements will be used in the analysis. ECG data will be listed by treatment, subject and visit/time.

For ECGs, a notable QTc value is defined as a QTcF (Fridericia) interval of \geq 450 msec for males or \geq 460 msec for females.

Clinical laboratory evaluations

All laboratory data will be listed by treatment, subject, and visit/time, if normal ranges are available, abnormalities will be flagged. Summary statistics will be provided by treatment and visit/time.

Adverse events

All information obtained on adverse events will be displayed by treatment group and subject.

Summary tables for adverse events (AEs) will summarize only on-treatment events, with a start date during the on-treatment period (treatment-emergent AEs).

The on-treatment period lasts from the date of first administration of study treatment to 1 week after the last actual administration of any study treatment.

The number (and percentage) of subjects with treatment emergent adverse events (events started after the first dose of study medication or events present prior to start of double-blind treatment but increased in severity based on preferred term) will be summarized by treatment, primary system organ class, preferred term and maximum severity.

Separate summaries will be provided for study medication related adverse events, death including on treatment and post treatment (30 days after the last actual administration of study treatment), serious adverse events, other significant adverse events leading to discontinuation.

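### The 7-day cut for safety summaries falls on the nominal End of Study day, so whether EoS ECGs and vital signs are summarised depends on the appointment date, and non-fatal SAEs on post-dose days 8 to 30 have no clear by-arm table

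*SAP*

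**What the plan says.** **The filter.** SAP section 7 says: "Safety summaries include only data from the on-treatment period with the exception of baseline data". SAP 7.2 (Adverse events) runs the on-treatment period from the first dose "to 1 week after the last actual administration of any study treatment". Protocol 12.5.2 has the same restriction and the same limit: "to one week after the date of the last actual administration of any study treatment". AE tables count only events that start inside that period.

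**The last dose.** Protocol 3.1: "The morning dose on Day 84 will be the final dose administration for this treatment period". The Day 84 visit carries a ±3-day window in Table 8-1. Dosing can also run on if no spontaneous sputum is obtained: "site needs to reschedule the visit within 3 days after Day 84 and subject must continue to take study medication". A delayed HRCT has the same effect.

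**The EoS visit.** Protocol 3.1: "Approximately one week upon completion of the treatment period, subjects will be invited to the center". Table 8-1 places it at Day 91 ±3 and marks ECG, blood pressure, pulse and temperature. The laboratory safety panels are not marked at that visit.

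**Planned outputs.** Protocol 12.5.2 plans descriptive statistics by treatment and visit for both vital signs and ECG. The SAP's own paragraphs on these two domains name only listings, although the opening of SAP 7.2 specifies descriptive statistics for continuous safety data in general.

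**SAEs and deaths.** Under protocol 10.1.3, SAEs occurring after consent and "until 30 days following the last administration of study treatment must be reported". Deaths up to 30 days after the last dose have their own summary (protocol 12.5.2; SAP 7 and 7.2). SAP 7.2 also promises listings of all AEs and SAEs.

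**The concern.** The analysis cut-off and the nominal date of a scheduled visit are the same day, and that visit is allowed to happen up to three days later. Two patients who both follow the protocol can then be treated differently: one seen on Day 91 contributes an EoS ECG and vital signs to the summary, and one seen on Day 92 does not. Any EoS column would describe a subset picked by appointment date. I found no visit-assignment rule in the SAP that would keep the later record.

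For SAEs, the collection window (30 days) and the AE tabulation window (7 days) differ. Deaths were given a 30-day summary to bridge that gap. Non-fatal SAEs were not clearly given one.

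Safety description matters relatively more here. The SAP drops the Bayesian model, the secondary modelling and the PK/PD analysis because the study was terminated, and it notes the low sample size. In small arms, a few omitted records can visibly change a by-visit summary.

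**Working it through.** **1. The plan's own dates.** Last dose Day 84 + 7 = Day 91, the nominal EoS day. Day 84 + 30 = Day 114, the safety call. Both reproduce.

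**2. EoS days left out.** Let L be the day of the last dose. The on-treatment period ends on day L + 7. The EoS window is Days 88 to 94, which is 7 days. A visit is left out of the summaries if EoS day > L + 7, so for L from 81 to 87 the number left out is 94 − (L + 7) = 87 − L.

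| Last dose (L) | Period ends | EoS days left out | Count of 7 |
|---|---|---|---|
| 81 | 88 | 89–94 | 6 |
| 82 | 89 | 90–94 | 5 |
| 83 | 90 | 91–94 | 4 |
| **84 (planned)** | **91** | **92–94** | **3** |
| 85 | 92 | 93–94 | 2 |
| 86 | 93 | 94 | 1 |
| 87 | 94 | none | 0 |

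Rows 81 to 83 assume that dosing ends at a Day 84 visit held early within its window. Rows 85 to 87 correspond to a late visit or to the permitted extension of dosing.

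Over all pairs: 6 + 5 + 4 + 3 + 2 + 1 + 0 = 21 of 7 × 7 = 49, or 43%. The planned row alone gives 3/7, also 43%. The longest in-window gap is 94 − 81 = 13 days; with the last dose on Day 84 it is 94 − 84 = 10 days.

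**3. Visits outside this table.** Patients who stop treatment early are asked, where possible, to return for the EoS assessments (protocol 9.1.1), and protocol section 8 asks for the final visit of early leavers as soon as possible. I found no upper limit tying that visit to the last dose, so these records can also fall past the cut. The documents give no basis for counting them.

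**4. SAE windows.** Post-dose days 8 to 30 number 30 − 8 + 1 = 23 of the 30 collection days. For an SAE starting in that span:

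- Fatal within 30 days: included in the 30-day death summary. SAP 7.2 also tabulates deaths from SAEs by system organ class and preferred term.
- Non-fatal: outside the on-treatment AE and SAE tables, but in the listings.
- Non-fatal and suspected to be related: unclear. The registry-disclosure paragraph in SAP 7.2 attaches the on-treatment label to SAEs in general, and then names related SAEs without repeating it.

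**5. Exposure.** Protocol 4.2 gives a half-life of 10–16 hours. Seven days is 168 h: 168/16 = 10.5 and 168/10 = 16.8 half-lives.

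**The case against.** The strongest reply is that this is a pre-specified reporting convention, the same in protocol and SAP, and that nothing goes unreported. That is correct. All AEs and SAEs are listed, ECGs and vital signs are listed by subject and visit, and vital-sign abnormalities are flagged. In a small terminated trial, listings can be read in full. Seven days is also more than ten half-lives, so it is a generous window for treatment-emergent events, and there is no case for changing it there.

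Second, the EoS column is partly inferred. The SAP paragraphs on ECG and vital signs promise only listings; a by-visit table follows from the general text of SAP 7.2 and from protocol 12.5.2. This narrows the point, but the protocol does plan those summaries and the SAP does not withdraw them.

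Third, a reader might infer that 43% of EoS records would be lost. The documents do not support that. The figure counts calendar days or pairs, and becomes a share of patients only if visits spread evenly and, for the 49 pairs, independently. Protocol 3.1 ties EoS to about one week after treatment ends, so a site that moves Day 84 would probably move EoS too. The 13-day gap is an extreme combination.

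Fourth, a reader might infer that every SAE from days 8 to 30 leaves the tables. Fatal cases are kept, and the wording on related SAEs is open. The 23 of 30 days say nothing about the share of events.

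Fifth, a reader might infer bias between arms. Subjects and investigators are blinded, and the documents suggest no reason why appointment dates would differ by arm. Body weight, although measured at EoS, is not among the post-baseline variables in SAP 7.1, so it is not affected.

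**Conclusion.** The point holds in a limited form, and its severity is minor. Applied as written, the 7-day filter makes inclusion of EoS ECG and vital-sign data in the by-visit summaries depend on scheduling. With the last dose on Day 84, 3 of the 7 permitted EoS days fall outside; the range is 0 to 6 of 7 for last doses from Day 87 back to Day 81. This rests on reading protocol 12.5.2 as still requiring those summaries, and on there being no unstated rule that assigns EoS by nominal visit.

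Non-fatal SAEs with onset on post-dose days 8 to 30 are collected and listed but have no clearly specified by-arm summary.

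The protocol and SAP agree on the cut-off, so this is a gap in the reporting window. It is neither a contradiction nor an error of calculation. How many patients or events are affected cannot be derived from the documents.

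**What to change.** 1. In SAP section 7, add: by-visit summaries of ECG and vital signs include the EoS visit under its nominal visit label, whatever the interval from the last dose.
2. Add one table, by arm, of SAEs with onset 8 to 30 days after the last dose, labelled post-treatment and kept apart from the treatment-emergent tables.
3. In the registry-disclosure paragraph of SAP 7.2, state which time window applies to SAEs suspected to be related.
4. Keep the 7-day rule for treatment-emergent AEs.
5. Record in the SAP that items 1 and 2 depart from the on-treatment restriction in protocol 12.5.2, or align that section.

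The cost is a small amount of programming (one date filter lifted for two domains and one short table) and a documented departure from the protocol wording. No new data are needed.

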7.1 Variables

Adverse events, vital signs (blood pressure, pulse rate, body temperature), ECG intervals, laboratory measurements, as well as subject demographics, baseline characteristics, and treatment information.

7.2 Descriptive analyses

Categorical data will be presented as frequencies and percentages. For continuous data, mean, standard deviation, median, minimum, and maximum will be presented. Day 1 is defined as the date of first study drug administration. Study day is calculated relative to Day 1.

Subject demographics and other baseline characteristics

Demographic, including age, sex, race, ethnicity, and other baseline data including, baseline height, baseline weight, baseline BMI, past medical history including smoking history, history of bronchiectasis exacerbations and current medical conditions including allergies present

before signing the informed consent will be summarized descriptively by treatment group for the Safety set, if data allows.

BMI (kg/m^2) = Weight (kg) / [Height (m) * Height (m)]

All data for background and demographic variables will be listed by treatment group and subject. Summary statistics will be provided by treatment group. Continuous variables will be summarized using descriptive statistics (mean, SD, median, minimum and maximum) and categorical variables will be summarized in terms of the number and percentage of subjects in each category.

Medical history was coded using the Medical Dictionary for Regulatory Activities (MedDRA) terminology. History/conditions will be summarized for the safety analysis set, by primary system organ class and preferred term, and overall. Verbatim recorded history/conditions will be listed together with the coded terms, date of diagnosis/surgery and whether the problem was active at the time of first study drug dose.

Subject disposition

A disposition summary will be presented for all subjects in the safety analysis set. This table will present the number and percentage of subjects who randomized, completed and discontinued early, along with the reasons for early discontinuation.

The number and percentage of subjects in each analysis set will be summarized by treatment group. All analysis set results will be presented in listings by subject. A separate listing of all subjects excluded from any analysis set and the reasons for their exclusion will be provided.

All study completion data will be listed by subject.

Treatment

Data for study drug administration, rescue medication and concomitant therapies will be listed by treatment group and subject.

Summary statistics will be provided for the duration of exposure to study treatment using the safety analysis set.

Concomitant medications and significant non-drug therapies prior to and after the start of the study treatment will be listed and summarized according to the Anatomical Therapeutic Chemical (ATC) classification system, by treatment group.

Vital signs

Records taken at baseline visit will be considered as baseline value. Otherwise, records take at Day 1 will be considered as baseline value. Vital sign data for all subjects will be listed by treatment group, subject and visit/time, and abnormalities will be flagged. The normal range of vital signs are:

Oral body temperature: 36.5-37.5 °C
Systolic blood pressure: 90-140 mm Hg
Diastolic blood pressure: 50-90 mm Hg

• Pulse rate: 50 - 100 bpmD

ECG evaluations

ECG data will be collected at scheduled visits in single ECG or triplicate ECGs. If triplicate ECGs are performed, then average of the non-missing values of the 3 measurements will be used in the analysis. ECG data will be listed by treatment, subject and visit/time.

For ECGs, a notable QTc value is defined as a QTcF (Fridericia) interval of \geq 450 msec for males or \geq 460 msec for females.

Clinical laboratory evaluations

All laboratory data will be listed by treatment, subject, and visit/time, if normal ranges are available, abnormalities will be flagged. Summary statistics will be provided by treatment and visit/time.

Adverse events

All information obtained on adverse events will be displayed by treatment group and subject.

Summary tables for adverse events (AEs) will summarize only on-treatment events, with a start date during the on-treatment period (treatment-emergent AEs).

The on-treatment period lasts from the date of first administration of study treatment to 1 week after the last actual administration of any study treatment.

The number (and percentage) of subjects with treatment emergent adverse events (events started after the first dose of study medication or events present prior to start of double-blind treatment but increased in severity based on preferred term) will be summarized by treatment, primary system organ class, preferred term and maximum severity.

Separate summaries will be provided for study medication related adverse events, death including on treatment and post treatment (30 days after the last actual administration of study treatment), serious adverse events, other significant adverse events leading to discontinuation.

A subject with multiple adverse events within a primary system organ class is only counted once towards the total of the primary system organ class. Listings will be provided for all AEs, SAEs and fatal AEs.

For the legal requirements of ClinicalTrials.gov and EudraCT, two required tables on treatment emergent adverse events which are not serious adverse events with an incidence greater than 5% and on-treatment emergent serious adverse events and SAE suspected to be related to study treatment will be provided by system organ class and preferred term on the safety set population.

If for a same patient, several consecutive AEs (irrespective of study treatment causality, seriousness and severity) occurred with the same SOC and PT:

• a single occurrence will be counted if there is ≤ 1 day gap between the end date of the preceding AE and the start date of the consecutive AE

• more than one occurrence will be counted if there is > 1 day gap between the end date of the preceding AE and the start date of the consecutive AE.

For occurrence, the presence of at least one SAE / SAE suspected to be related to study treatment / non-SAE has to be checked in a block e.g., among AE's in a \leq 1 day gap block, if at least one SAE is occurring, then one occurrence is calculated for that SAE.

The number of deaths resulting from SAEs suspected to be related to study treatment and SAEs irrespective of study treatment relationship will be provided by SOC and PT.
